## Table 14.1-1.4.2 Demographics and Baseline Characteristics (Full Analysis Set)

Same layout as Table 14.1-1.4.1. Use the following footnote.

[1] P-value is for testing the null hypotheses that summary statistics (mean or proportion) are equal among treatment groups. All tests are two-sided. \* indicates statistical significance at 0.05 level.

Source Data: Listing 16.2-4.1

Table 14.1-1.4.3

Demographics and Baseline Characteristics
(Per Protocol Analysis Set)

Same layout as Table 14.1-1.4.1. Use the following footnote.

[1] P-value is for testing the null hypotheses that summary statistics (mean or proportion) are equal among treatment groups. All tests are two-sided. \* indicates statistical significance at 0.05 level.

Source Data: Listing 16.2-4.1

Table 14.1-1.4.4

Demographics and Baseline Characteristics by Country
(Safety Analysis Set)

Same layout as Table 14.1-1.4.1. Display 'Country: United States' on the header of the table. Use the following footnote.

[1] P-value is for testing the null hypotheses that summary statistics (mean or proportion) are equal among treatment groups. All tests are two-sided. \* indicates statistical significance at 0.05 level.

Source Data: Listing 16.2-4.1

Table 14.1-1.5 Substance Use (Safety Analysis Set)

	EGT0001442 (N=xxx)	Placebo (N=xxx)	Total (N=xxx)
Alcohol Consumption	xxx	xxx	xxx
n	xxx (xx.x%)	xxx (xx.x%)	xxx (xx.x%)
Yes	xxx (xx.x%)	xxx (xx.x%)	xxx (xx.x%)
No			
Alcohol Units Consumed Per Week			
n	xxx	xxx	xxx
Mean (SD)	xx.x (xx.xx)	xx.x (xx.xx)	xx.x (xx.xx
Median	xx.x	xx.x	xx.x
Min, Max	xx, xx	xx, xx	xx, xx
Tobacco Use			
n	xxx	XXX	XXX
Never Used	xxx (xx.x%)	xxx (xx.x%)	xxx (xx.x%)
Current User	xxx (xx.x%)	xxx (xx.x%)	xxx (xx.x%)
Former User	xxx (xx.x%)	xxx (xx.x%)	xxx (xx.x%)
Drug Dependency or Abuse	xxx	xxx	xxx
n	xxx (xx.x%)	xxx (xx.x%)	xxx (xx.x%)
Yes	xxx (xx.x%)	xxx (xx.x%)	xxx (xx.x%)
No			

Source Data: Listing 16.2-4.2

Protocol: THR-1442-C-418 Page x of y

Table 14.1-2.1 Medical History (Safety Analysis Set)

	EGT0001442 (N=xxx)	Placebo (N=xxx)
Subjects with Any Conditions	xxx (xx.x%)	xxx (xx.x%)
xxxxxxx	xxx (xx.x%)	xxx (xx.x%)
XXXXXXX	xxx (xx.x%)	xxx (xx.x%)
OTHER	xxx (xx.x%)	xxx (xx.x%)

Source Data: Listing 16.2-4.4

### Table 14.1-2.2 Diabetes Disease History (Safety Analysis Set)

	EGT0001442 (N=xxx)	Placebo (N=xxx)
Duration of Diabetes (years) [1]		
n	xxx	xxx
Mean (SD)	xx.x (xx.xxx)	xx.x (xx.xxx)
Median	xx.x	xx.x
Min, Max	xx, xx	xx, xx
Baseline Diabetes Therapy		
n	xxx	XXX
Treatment Naive	xxx (xx.x%)	xxx (xx.x%)
Treated with One Anti-diabetic Agent	xxx (xx.x%)	xxx (xx.x%)
Blindness		
n	xxx	xxx
Yes	xxx (xx.x%)	xxx (xx.x%)
No	xxx (xx.x%)	xxx (xx.x%)
Cataracts		
Retinopathy		
Laser Treatment to Either Eye		
Foot Ulceration		
Peripheral Neuropathy		
Lower Limb Amputation		
Diabetic Nephropathy		
Current Microalbuminuria		
Current Proteinuria		
Dialysis		
Kidney Transplantation		
Major Hypoglycemic Event		
Documented Hypoglycemic Event		

 To calculate duration from a partial diagnosis date, a missing month is imputed as January and a missing day is imputed as the first of the month.

Source Data: Listings 16.2-4.4 and 16.2-4.5

Protocol: THR-1442-C-418 Page x of y

## Table 14.1-2.3 Diabetes Disease History by Country (Safety Analysis Set)

Same layout as Table 14.1-2.3. Display 'Country: United States' on the header of the table. Use the following footnote

[1] To calculate duration from a partial diagnosis date, a missing month is imputed as January and a missing day is imputed as the first of the month.

Source Data: Listings 16.2-4.4 and 16.2-4.5

<DIRECTORY PATH>PROGRAM NAME Executed: DDMMMYYYY hh:mm Data Extracted: DDMONYYYY

Final - 22November2011 CONFIDENTIAL Page 20 of 106

Table 14.1-3.1 Prior Medications (Safety Analysis Set)

TC Level 4 Term Preferred Term	EGT0001442 (N=xxx)	Placebo (N=xxx)
Subjects with Any Medications	xxx (xx.x%)	xxx (xx.x%)
TC Level 4 Term #1	xxx (xx.x%)	xxx (xx.x%)
Preferred Term #1	xxx (xx.x%)	xxx (xx.x%)
Preferred Term #2	xxx (xx.x%)	xxx (xx.x%)
TC Level 4 Term #2	xxx (xx.x%)	xxx (xx.x%)
XXXXX	xxx (xx.x%)	xxx (xx.x%)
XXXXX	xxx (xx.x%)	xxx (xx.x%)
XXXXX	xxx (xx.x%)	xxx (xx.x%)
XXXXX	xxx (xx.x%)	xxx (xx.x%)
XXXXX	xxx (xx.x%)	xxx (xx.x%)

Note: At each level of summarization, a subject is counted once if the subject reported one or more medications.

Medications are coded using WHODRUG enhanced version June 2011. Prior medications are those started before the first dose of study medication.

Source Data: Listing 16.2-5.1

Table 14.1-3.2 Concomitant Medications (Safety Analysis Set)

TC Level 4 Term Preferred Term	EGT0001442 (N=xxx)	Placebo (N=xxx)
ubjects with Any Medications	xxx (xx.x%)	xxx (xx.x%)
TC Level 4 Term #1	xxx (xx.x%)	xxx (xx.x%)
Preferred Term #1	xxx (xx.x%)	xxx (xx.x%)
Preferred Term #2	xxx (xx.x%)	xxx (xx.x%)
TC Level 4 Term #2	xxx (xx.x%)	xxx (xx.x%)
XXXX	xxx (xx.x%)	xxx (xx.x%)
XXXX	xxx (xx.x%)	xxx (xx.x%)
XXXXX	xxx (xx.x%)	xxx (xx.x%)
XXXXX	xxx (xx.x%)	xxx (xx.x%)
XXXXX	xxx (xx.x%)	xxx (xx.x%)

Note: At each level of summarization, a subject is counted once if the subject reported one or more medications.

Medications are coded using WHODRUG enhanced version June 2011. Concomitant medications are those taken at any time on or after the day of the first dose of study medication, including those started prior to randomization but were continuing during the study period.

Source Data: Listing 16.2-5.1

Protocol: THR-1442-C-418 Page x of y

Table 14.1-3.3
Hyperglycemia Rescue Medications
(Safety Analysis Set)

ATC Level 4 Term Preferred Term	EGT0001442 (N=xxx)	Placebo (N=xxx)
rielelied leim	(IV-XXX)	(N-XXX)
Subjects with Any Rescue Medications	xxx (xx.x%)	xxx (xx.x%)
ATC Level 4 Term #1	xxx (xx.x%)	xxx (xx.x%)
Preferred Term #1	xxx (xx.x%)	xxx (xx.x%)
Preferred Term #2	xxx (xx.x%)	xxx (xx.x%)
ATC Level 4 Term #2	xxx (xx.x%)	xxx (xx.x%)
XXXXXX	xxx (xx.x%)	xxx (xx.x%)
XXXXXX	xxx (xx.x%)	xxx (xx.x%)
XXXXXX	xxx (xx.x%)	xxx (xx.x%)
XXXXXX	xxx (xx.x%)	xxx (xx.x%)
XXXXXX	xxx (xx.x%)	xxx (xx.x%)

Note: Only concomitant anti-hyperglycemia medications that are indicated by the investigator as being used for hyperglycemia rescue are included in this summary. At each level of summarization, a subject is counted once if the subject reported one or more medications. Medications are coded using WHODRUG enhanced version June 2011. Concomitant rescue medications are those taken at any time on or after the day of the first dose of study medication.

Source Data: Listing 16.2-5.1

Table 14.1-3.4

Proportion of Subjects with Hyperglycemia Rescue (Safety Analysis Set)

	EGT0001442 (N=xxx)	Placebo (N=xxx)
umber of Subjects Rescued by Time of First Rescue		
<=2 weeks	xxx (xx.x%)	xxx (xx.x%)
>2 weeks - <=6 weeks	xxx (xx.x%)	xxx (xx.x%)
>6 weeks - <=12 weeks	xxx (xx.x%)	xxx (xx.x%)
>12 weeks - <=18 weeks	xxx (xx.x%)	xxx (xx.x%)
>18 weeks - <=24 weeks	xxx (xx.x%)	xxx (xx.x%)
>24 weeks - <=36 weeks	xxx (xx.x%)	xxx (xx.x%)
>36 weeks - <=48 weeks	xxx (xx.x%)	xxx (xx.x%)
>48 weeks - <=60 weeks	xxx (xx.x%)	xxx (xx.x%)
>60 weeks - <=72 weeks	xxx (xx.x%)	xxx (xx.x%)
>72 weeks - <=84 weeks	xxx (xx.x%)	xxx (xx.x%)
>84 weeks - <=96 weeks	xxx (xx.x%)	xxx (xx.x%)

Source Data: Listing 16.2-5.1

Table 14.1-4.1 Treatment Exposure (Safety Analysis Set)

	EGT0001442 (N=xxx)	Placebo
		(N=xxx)
Ouration of Exposure (weeks)		
n	xxx	xxx
Mean (SD)	xx.x (xx.xxx)	xx.x (xx.xxx)
Median	xx.x	xx.x
Min, Max	xx, xx	xx, xx
Jumber (%) of Subjects with Exposure of		
1 Dose	xxx (xx.x%)	xxx (xx.x%)
>1 Dose - <=2 weeks	xxx (xx.x%)	xxx (xx.x%)
>2 weeks - <=6 weeks	xxx (xx.x%)	xxx (xx.x%)
>6 weeks - <=12 weeks	xxx (xx.x%)	xxx (xx.x%)
>12 weeks - <=18 weeks	xxx (xx.x%)	xxx (xx.x%)
>18 weeks - <=24 weeks	xxx (xx.x%)	xxx (xx.x%)
>24 weeks - <=36 weeks	xxx (xx.x%)	xxx (xx.x%)
>36 weeks - <=48 weeks	xxx (xx.x%)	xxx (xx.x%)
>48 weeks - <=60 weeks	xxx (xx.x%)	xxx (xx.x%)
>60 weeks - <=72 weeks	xxx (xx.x%)	xxx (xx.x%)
>72 weeks - <=84 weeks	xxx (xx.x%)	xxx (xx.x%)
>84 weeks - <=96 weeks	xxx (xx.x%)	xxx (xx.x%)
>96 weeks	xxx (xx.x%)	xxx (xx.x%)

Note: Duration of exposure (weeks) =  $(date\ of\ last\ dose\ -\ date\ of\ first\ dose\ +\ 1)/7.$ 

Source Data: Listing 16.2-6.1

[figure not shown]
Protocol: THR-1442-C-418 Page x of y

[figure not shown]
Table 14.1-4.2 Treatment Compliance (Safety Analysis Set)

	EGT0001442	Placebo
	(N=xxx)	(N=xxx)
Compliance (%)		
n	XXX	xxx
Mean (SD)	xx.x (xx.xxx)	xx.x (xx.xxx)
Median	xx.x	xx.x
Min, Max	xx, xx	xx, xx
Compliance Category		
n	XXX	xxx
<80%	xxx (xx.x%)	xxx (xx.x%)
>=80%	xxx (xx.x%)	xxx (xx.x%)

Note: Treatment compliance is calculated as total number of administered capsules divided by total number of capsules which should have been taken based on the last completed visit during active treatment period.

Source Data: Listing 16.2-6.1

Source Data: Table 14.2-1.3

Programming Note: Display treatment group identifiers identical to those in summary tables instead of using TRT A and TRT B as shown in the shell. Also, this shell only shows through Week 52 but our data and plot will go through Week 97.

Protocol: THR-1442-C-418 Page x of y

Figure 14.2-1.2
Line Graph of Mean (+/- SE) HbAlc (%), Excluding Post-Rescue Values
(Full Analysis Set - OC)

See Figure 14.2-1.1 for layout and general programming notes. Use footnotes below.

Source Data: Table 14.2-1.3

Figure 14.2-2.1

Line Graph of Mean (+/-SE) Change from Baseline in Fasting Plasma Glucose (mmol/L), Excluding Post-Rescue Values (Full Analysis Set - OC)

See Figure 14.2-1.1 for layout and general programming notes. Use footnotes below.

Source Data: Table 14.2-2.3

Figure 14.2-2.2

Line Graph of Mean (+/- SE) Fasting Plasma Glucose (mmol/L), Excluding Post-Rescue Values (Full Analysis Set - OC)

See Figure 14.2-1.1 for layout and general programming notes. Use footnotes below.

Source Data: Table 14.2-2.3

Protocol: THR-1442-C-418 Page x of y

Figure 14.2-3.1

Line Graph of Mean (+/- SE) Change from Baseline in Weight (kg), Excluding Post-Rescue Values (Full Analysis Set - OC)

See Figure 14.2-1.1 for layout and general programming notes. Use footnotes below.

Source Data: Table 14.2-3.3

Figure 14.2-3.2

Line Graph of Mean (+/- SE) Weight (kg), Excluding Post-Rescue Values (Full Analysis Set - OC)

See Figure 14.2-1.1 for layout and general programming notes. Use footnotes below.

Source Data: Table 14.2-3.3

Figure 14.2-4.1

Line Graph of Mean (+/- SE) Change from Baseline in Systolic Blood Pressure (mmHg), Excluding Post-Rescue Values (Full Analysis Set - OC)

See Figure 14.2-1.1 for layout and general programming notes. Use footnotes below.

Source Data: Table 14.2-4.3

Protocol: THR-1442-C-418 Page x of y

Figure 14.2-4.2

Line Graph of Mean (+/- SE) Systolic Blood Pressure (mmHg), Excluding Post-Rescue Values (Full Analysis Set - OC)

See Figure 14.2-1.1 for layout and general programming notes. Use footnotes below.

Source Data: Table 14.2-4.3

Figure 14.2-5.1

Line Graph of Mean (+/- SE) Change from Baseline in Diastolic Blood Pressure (mmHg), Excluding Post-Rescue Values (Full Analysis Set - OC)

See Figure 14.2-1.1 for layout and general programming notes. Use footnotes below.

Source Data: Table 14.2-5.3

Figure 14.2-5.2

Line Graph of Mean (+/- SE) Diastolic Blood Pressure (mmHg), Excluding Post-Rescue Values (Full Analysis Set - OC)

See Figure 14.2-1.1 for layout and general programming notes. Use footnotes below.

Source Data: Table 14.2-5.3

## Table 14.2-1.1 Analysis of Change from Baseline in HbA1c (%) at Week 24 (Full Analysis Set - LOCF)

Week 24

	EGT0001442	Placebo
	(N=xxx)	(N=xxx)
Number of Subjects [1]	xxx	xxx
Number (%) of Values Carried Forward	xx (xx.x%)	xx (xx.x%)
Baseline		
Mean (SD)	xx.xx (xx.xxx)	xx.xx (xx.xxx)
Median	xx.xx	xx.xx
Min, Max	xx.x, xx.x	xx.x, xx.x
Week 24		
Mean (SD)	xx.xx (xx.xxx)	xx.xx (xx.xxx)
Median	xx.xx	xx.xx
Min, Max	xx.x, xx.x	xx.x, xx.x
Change from Baseline		
Mean (SD)	xx.xx (xx.xxx)	xx.xx (xx.xxx)
Median	xx.xx	xx.xx
Min, Max	xx.x, xx.x	xx.x, xx.x
p-value [2]	0.xxxx	
Model-Adjusted Change from Baseline [3]		
LS Mean (SE)	xx.xx (xx.xxx)	xx.xx (xx.xxx)
95% Confidence Interval	(xx.xx, xx.xx)	(xx.xx, xx.xx)
Difference from Placebo [3]		
Difference of LS Means	xx.xx	
95% Confidence Interval	(xx.xx, xx.xx)	
p-value	0.xxxx	

Note: This analysis uses the last observation carried forward (LOCF) method for missing post-baseline values as well as for values obtained after hyperglycemia rescue. \* indicates statistical significance at 0.05 level.

- [1] Number of subjects with a value at baseline and at the specified visit.
- [2] The p-value is from a two-sided t-test for the difference in means of change from baseline.
- [3] Based on ANCOVA: Change = trt + baseline HbAlc + site + age category + gender + race.

Source Data: Listing 16.2-7.1

Table 14.2-1.2

Analysis of Change from Baseline in HbA1c (%)
(Full Analysis Set - LOCF)

Week 2

	EGT0001442	Placebo	
	(N=xxx)	(N=xxx)	
Number of Subjects [1]	xxx	xxx	
Number (%) of Values Carried Forward	xx (xx.x%)	xx (xx.x%)	
Baseline			
Mean (SD)	xx.xx (xx.xxx)	xx.xx (xx.xxx)	
Median	xx.xx	xx.xx	
Min, Max	xx.x, xx.x	xx.x, xx.x	
Week 2			
Mean (SD)	xx.xx (xx.xxx)	xx.xx (xx.xxx)	
Median	xx.xx	xx.xx	
Min, Max	xx.x, xx.x	xx.x, xx.x	
Change from Baseline			
Mean (SD)	xx.xx (xx.xxx)	xx.xx (xx.xxx)	
Median	xx.xx	xx.xx	
Min, Max	xx.x, xx.x	xx.x, xx.x	
p-value [2]	0.xxxx		
Model-Adjusted Change from Baseline [3]			
LS Mean (SE)	xx.xx (xx.xxx)	xx.xx (xx.xxx)	
95% Confidence Interval	(xx.xx, xx.xx)	(xx.xx, xx.xx)	
Difference from Placebo [3]			
Difference of LS Means	xx.xx		
95% Confidence Interval	(xx.xx, xx.xx)		
p-value	0.xxxx		

Note: This analysis uses the last observation carried forward (LOCF) method for missing post-baseline values as well as for values obtained after hyperglycemia rescue. \* indicates statistical significance at 0.05 level.

- [1] Number of subjects with a value at baseline and at the specified visit.
- [2] The p-value is from a two-sided t-test for the difference in means of change from baseline.
- [3] Based on ANCOVA: Change = trt + baseline HbAlc + site + age category + gender + race.

Source Data: Listing 16.2-7.1

Programming Note: present for Weeks 2, 6, 12, 18, 24, 36, 48, 60, 72, 84, 96, 97 and 1 week follow-up.

Table 14.2-1.3

Analysis of Change from Baseline in HbA1c (%), Excluding Post-Rescue Values (Full Analysis Set - OC)

Week 2

	EGT0001442	Placebo
	(N=xxx)	(N=xxx)
Number of Subjects [1]	xxx	xxx
Baseline		
Mean (SD)	xx.xx (xx.xxx)	xx.xx (xx.xxx)
Median	xx.xx	xx.xx
Min, Max	xx.x, xx.x	xx.x, xx.x
Week 2		
Mean (SD)	xx.xx (xx.xxx)	xx.xx (xx.xxx)
Median	xx.xx	xx.xx
Min, Max	xx.x, xx.x	xx.x, xx.x
Change from Baseline		
Mean (SD)	xx.xx (xx.xxx)	xx.xx (xx.xxx)
Median	xx.xx	xx.xx
Min, Max	xx.x, xx.x	xx.x, xx.x
p-value [2]	0.xxxx	
Model-Adjusted Change from Baseline [3]		
LS Mean (SE)	xx.xx (xx.xxx)	xx.xx (xx.xxx)
95% Confidence Interval	(xx.xx, xx.xx)	(xx.xx, xx.xx)
Difference from Placebo [3]		
Difference of LS Means	xx.xx	
95% Confidence Interval	(xx.xx, xx.xx)	
p-value	0.xxxx	

Note: This analysis uses observed values excluding those obtained after hyperglycemia rescue; no missing data imputation is performed. \* indicates statistical significance at 0.05 level.

- [1] Number of subjects with a value at baseline and at the specified visit.
- [2] The p-value is from a two-sided t-test for the difference in means of change from baseline.
- [3] Based on ANCOVA: Change = trt + baseline HbAlc + site + age category + gender + race.

Source Data: Listing 16.2-7.1

Programming Note: present for Weeks 2, 6, 12, 18, 24, 36, 48, 60, 72, 84, 96, 97 and 1 week follow-up.

Table 14.2-1.4

Repeated Measures Analysis of Change from Baseline in HbAlc (%) at Week 96, Excluding Post-rescue Values (Full Analysis Set - OC)

	EGT0001442 (N=xxx)	Placebo (N=xxx)
Model-Adjusted Change from Baseline at Week 96 [1]		
n (# of Subjects)	xx	xx
k (# of Post-baseline Visits)	xx	xx
LS Mean (SE)	xx.xx (xx.xxx)	xx.xx (xx.xxx)
95% Confidence Interval	(xx.xx, xx.xx)	(xx.xx, xx.xx)
Difference from Placebo [1]		
Difference of LS Means	xx.xx	
95% Confidence Interval	(xx.xx, xx.xx)	
p-value	0.xxxx	

Note: This analysis uses all observed values excluding those obtained after hyperglycemia rescue; no missing data imputation is performed. \* indicates statistical significance at 0.05 level.

Source Data: Listing 16.2-7.1

 $\ensuremath{\texttt{[1]}}$  Based on repeated measure model including treatment and visit as factors.

Protocol: THR-1442-C-418 Page x of y

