**Table 2: Analysis Visit Windows** 

Scheduled Visit	Target Study Day of Visit	Slotting Intervals
Week -5 (Screening)	-35	<=-25
Week -2	-14	-24 to -4 days
Baseline (Week 0)	1	-3 to 1 days
Week 2	15	2 to 29 days
Week 6	43	30 to 64 days
Week 12	85	65 to 106 days
Week 18	127	107 to 148 days
Week 24	169	149 to 211 days
Week 36	253	212 to 295 days
Week 48	337	296 to 379 days
Week 60	421	380 to 463 days
Week 72	505	464 to 547 days
Week 84	589	548 to 631 days
Week 96 (End of Treatment	673	632 to (last dose date)
Visit)*		
Week 97**	680	>Last dose date + 7 days
1 Week Follow-up Visit**	Last dose date + 7 days	>Last dose date + 7 days

\* Week 96 is the end of treatment visit for those subjects completing the study per protocol. For subjects who withdraw early from active treatment, the end of treatment visit will be assigned to an analysis visit based on the visit slotting algorithm using study day.

For parameters which were not scheduled to be collected at all visits, still use the all-inclusive visit intervals defined for all visits (that is, the visit window table above) to slot records. However, if a value is slotted to a visit unscheduled for a parameter, it will not be summarized except for summaries focusing on extreme values such as laboratory shift tables. These records will also be included in data listings.

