#### **5.4.3** Multiple Evaluations

After all the records have been slotted based on study day, if there are multiple valid records for an assessment within an assigned analysis visit, only one of these records will be used for summary statistics and analyses. The record to be used is determined using the following hierarchy (in decreasing order):

- the record closest to the target visit day
- the record with an original nominal visit that matches the analysis visit

\*\* Week 97 is the 1 week post-treatment follow-up visit for those subjects completing the study per protocol. The 1 Week Follow-up Visit is the 1 week post-treatment follow-up visit for those subjects who withdraw early from active treatment.

• the record earliest in time

For missing values prior to Week 24 where the LOCF algorithm is applied, it is always the last valid assessment on treatment carried forward even though this might not be the assessment obtained by the above hierarchy and used in the summaries by visit.

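### The by-visit efficacy tables require between-arm tests on a 1-week follow-up page that the SAP's visit-window table assigns to early withdrawals

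*SAP*

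**What the plan says.** The visit list in the shells for HbA1c over time (SAP Appendix 1, Tables 14.2-1.2, 1.3 and 1.6) is: "Programming Note: present for Weeks 2, 6, 12, 18, 24, 36, 48, 60, 72, 84, 96, 97 and 1 week follow-up". The FPG, systolic and diastolic shells and the HbA1c <7% shells use the same list. The weight shells use a shorter list with the same last two entries.

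Each page for a continuous endpoint has two between-arm tests. The footnotes describe them as "The p-value is from a two-sided t-test for the difference in means of change from baseline" and, for HbA1c, "Based on ANCOVA: Change = trt + baseline HbAlc + site + age category + gender + race". The page also shows the adjusted difference from placebo with its 95% confidence interval, and an asterisk that "indicates statistical significance at 0.05 level". The HbA1c <7% pages have a chi-square p-value and the same asterisk.

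The footnote to SAP Table 2 (Analysis Visit Windows) separates the last two visits by who attends them: "Week 97 is the 1 week post-treatment follow-up visit for those subjects completing the study per protocol", and "The 1 Week Follow-up Visit is the 1 week post-treatment follow-up visit for those subjects who withdraw early from active treatment". The slotting interval for both is ">Last dose date + 7 days".

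The observed-case shells state: "This analysis uses observed values excluding those obtained after hyperglycemia rescue; no missing data imputation is performed". The SAP schedule of events has HbA1c, FPG, vital signs and a physical examination at Visit 15, which is held for early terminators as well as completers, so the page will have data. Nothing in the SAP makes it descriptive only.

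**The concern.** A between-arm test estimates an effect of randomised treatment when the arms being compared are those that randomisation produced. Here membership of the page depends on leaving treatment early, which happens after randomisation and may itself depend on treatment. The subjects are off drug, and their exposure can run from days to nearly 96 weeks. In the observed-case version, post-rescue values are removed as well.

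If the reasons for leaving are related to outcome differently in the two arms, the test can flag a difference when the drug does nothing, or hide one that exists. The reader of the table would see a confidence interval and perhaps an asterisk, in the same layout as the Week 24 page.

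**Working it through.** **1. The plan's own figure.** SAP 3.5 assumes a difference of 0.4%, SD 1.0%, two-sided α of 0.05 and about 90% power. Then n = 2(1.960 + 1.282)² × 1.0² / 0.4² = 131.3, so 132 per arm. The SAP states 133 (noncentral-t power 90.1%) and protocol 9.2 states 131 (89.7%). Both reproduce. With 150 enrolled per arm, the allowance for loss is 150 − 133 = 17 per arm (SAP) or 150 − 131 = 19 (protocol). I use 17 as an assumed size for the follow-up page. The plan does not forecast withdrawals over 96 weeks.

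**2. Count of affected p-values on the 1-week follow-up page.**

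| Tables | Number | p-values each | Total |
|---|---|---|---|
| Observed case: 14.2-1.3, 2.3, 3.3, 4.3, 5.3 | 5 | 2 | 10 |
| Observed case, HbA1c <7%: 14.2-6.2 | 1 | 1 | 1 |
| LOCF: 14.2-x.2 and x.6, five endpoints | 10 | 2 | 20 |
| LOCF, HbA1c <7%: 14.2-6.1, 6.4 | 2 | 1 | 2 |

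That is 11 in six observed-case tables and 22 in 12 LOCF tables: 33 in 18 tables.

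**3. Who is on the page.**
- *Observed-case tables.* No imputation, so early withdrawals only.
- *LOCF tables.* SAP 5.3.1 stops imputation after Week 24, which again leaves early withdrawals only. SAP 7.2 (and 7.3.2 and 7.3.3) applies LOCF to all visits, and on that reading carried-forward values could also fill the page. The two rules conflict.
- *The interval.* It starts strictly after day +7, although the target is day +7. For a completer with last dose on day 673, the target is 673 + 7 = 680. The Week 97 interval starts after 680 and the Week 96 interval ends at 673, so a visit on day 680 falls in no window. For a withdrawal with last dose on day 100, a visit on day 107 goes to Week 18 (days 107 to 148). A visit on day 108 meets both the Week 18 and the follow-up interval, and no rule says which wins.

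**4. How far the test can mislead.** Simulation with no drug effect: 150 per arm, SD 1.0, about 17 withdrawals per arm on average, and a two-sample t-test among withdrawals. The log-odds of withdrawal rise by a slope of 0, or of 0.5 to 1.0 on placebo, per SD of the subject's own HbA1c change. Slopes and withdrawal numbers are assumptions.

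| Selection | Mean spurious difference | Rejection at 0.05 |
|---|---|---|
| Random in both arms | 0 | about 5% |
| Same slope in both arms | 0 | about 5% |
| Half the slope on active | −0.21 to −0.36 | about 10% to 18% (repeat runs: 9% to 19%) |
| Placebo only | −0.43 to −0.80 | about 23% to 63% |

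With 25% withdrawing (about 37 per arm), the placebo-only range is −0.36 to −0.64 and about 33% to 80%.

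**5. Power of the page.** With 17 per arm, the noncentral-t power for a true 0.4% difference is about 20%. A non-significant result there would say little either.

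**The case against.** Five points can be made for leaving the shells alone.

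- *The stakes are low.* SAP 5.2 calls these p-values nominal, the protocol calls the secondary endpoints exploratory, and Table 14.2-1.1, the primary table, has only Week 24. This stands. A reader might infer that the primary conclusion is at risk. It is not, because no decision rule uses the follow-up page.
- *The page may not hold only withdrawals.* A reader might count all 33 p-values as comparisons of dropouts. The documents support that outright for 11. For the other 22 it depends on which LOCF rule governs.
- *The false-positive rate is assumption-driven.* A reader might take 23% to 63% as the expected error rate. It needs selection on placebo only. The design makes the extreme case less likely: rescued subjects stay on study drug (protocol 5.2, SAP 3.1), and hyperglycaemia is not among the withdrawal reasons in protocol 6.11. If rescue is assumed to remove the highest 10% or 20% of changes in each arm, the placebo-only figures fall to about 16% or 12% (slope 0.5) and 38% or 23% (slope 1.0). The simulation covers HbA1c only.
- *Week 97 is a different case.* A reader might double the count to 66 by adding the Week 97 page. Those are completers one week off drug, close to the subjects on the Week 96 observed-case page. Their comparison is limited but not meaningless, and the simulation does not address it.
- *An asterisk is not certain.* It prints only if p < 0.05.

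None of this justifies a between-arm test on a page reserved for early withdrawals. Calling a p-value nominal deals with multiplicity. It does not restore the comparison that randomisation protected.

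**Conclusion.** The point holds for the 1-week follow-up page. As written, the plan orders between-arm tests in a group selected after randomisation: 11 p-values in six observed-case tables for certain, and 22 more in 12 LOCF tables if SAP 5.3.1 governs. The distortion is conditional. There is none under random or equal selection, and it can be large if withdrawal is tied to outcome in one arm only. The range quoted rests on about 17 withdrawals per arm and on assumed slopes, none of which the documents supply.

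This is a fault in secondary and exploratory output. Sample size and the Week 24 primary analysis are unaffected. The LOCF conflict and the Table 2 interval are separate drafting faults that decide who is on the page, and they need settling whatever is done about the tests.

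**What to change.** 1. In the programming notes of Tables 14.2-1.2, 1.3 and 1.6, their FPG, weight, systolic and diastolic counterparts, and 6.1, 6.2 and 6.4, make the 1-week follow-up page descriptive only: n, mean, SD, median and range (n and percentage for HbA1c <7%). Drop the t-test, chi-square, ANCOVA, confidence interval and asterisk there. Label the page: early withdrawals only, off treatment.
2. Reconcile SAP 5.3.1 with the LOCF-for-all-visits wording in 7.2 (and 7.3.2 and 7.3.3), stating which applies after Week 24.
3. Correct the Table 2 interval so that it includes its own +7 target day, and say which window takes precedence when an early withdrawal's off-treatment record also fits a numbered visit.
4. Label Week 97: completers, off treatment. Dropping its tests is optional; the SAP's objective for HbA1c over time ends at Week 96.

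The cost is wording in the SAP and the shells. No data are added, and no descriptive information is lost, because Tables 14.2-1.5, 2.5, 3.5, 4.5, 5.5 and 6.3 already summarise the same visits.
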